4.0 Enrollment/Randomization

Potential subjects will be identified during their pre-operative clinic visit. Physician-investigators will review medical chart and relevant pre-operative testing to make this determination. Potential subjects will then meet with a member of the study team to read the consent in detail and discuss the study in full.

After consent has been obtained, the study personnel obtaining consent will then obtain and assign the appropriate randomization for that subject. The patients will be randomized 1:1 to either standard laser lithotripsy or MOSES laser lithotripsy. Randomization will be performed using the redcap randomization application.

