5.0 Study Procedures

This is a blinded study. Our research coordinator will present to the OR prior to the surgeon to meet with OR staff. At this time, the coordinator will inform the OR staff which group the patient has been randomly assigned. OR staff will be educated to set the laser as instructed by the surgeon but not share whether the MOSES laser lithotripsy is being used. Surgeons will not be aware of the group assignment. The surgeons are only able to adjust the laser energy settings between 0.4-1.0 joules and 4-15 hertz. To control for stone fragment size, surgeons will have to use an 13 french ureteral access sheath independent of ureteral diameter. The MOSES setting is turned on with a touch pad attached to the laser unit. Once the surgeon is ready to laser fragment the stone, they will request that the laser be activated and provide the laser energy settings. The laser technician/nurse will follow randomization and add or remove the MOSES option. The surgeons will not be informed if they are using standard laser or MOSES augmented laser technology. At the conclusion of laser fragmentation, stone basket extraction will occur and once all fragments are removed, the patient will have a ureteral stent placed, awoken, extubated and transferred to the post anesthesia recovery unit. Objective data about laser settings, utilization time and total energy will be obtained at the conclusion of the case. Additionally, the circulating team will record the total OR time. Other variables of interest include blood loss, blood transfusion requirements and complications (utilizing Clavien-Dindo classification) with an expected rate of approximately 1-2%. Subjective grading of stone movement during laser fragmentation as well as stone migration will be recorded.

In addition to the intraoperative variables mentioned above, we will obtain clinical information including stone size, location, and stone analysis will be recorded.

6.0 Reporting of Adverse Events or Unanticipated Problems involving Risk to Participants or Others

All adverse events or unanticipated problems related to study participation will be reported in keeping with the IRB's guidelines regarding such events.

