8.0 Statistical Considerations

Overall OR duration may differ up to 10 min with an average OR time for URS estimated at approximately 1 hour. A power analysis with 80% power and an alpha of 0.05 requires a total recruitment of 106 patients with 53 patients in each treatment arm. Due to a 10% chance of withdrawal rate, the study will enroll 116 subjects for 106 subjects to complete the study. Statistical analysis of the obtained data will include a student T-test for comparison of two continuous variables and chi-squared for categorical variables. If enough events occur to warrant a multivariate analysis, a Cox regression utilizing forward selection will be performed.

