8.1 Endpoint Considerations

The primary endpoint of interest will reduction in total laser time and total OR time. Secondary endpoints will evaluate complication rates using the Clavien-Dindo score.

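### Chi-squared is the only test named for categorical variables, but complications are expected in just 1-2% of patients, too few for its approximation to hold and possibly none at all

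*Protocol*

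**What the plan says.** Section 8.0 of the protocol plans "a student T-test for comparison of two continuous variables and chi-squared for categorical variables". It mentions no continuity correction, exact test or rule for sparse tables.

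Section 8.1 states: "Secondary endpoints will evaluate complication rates using the Clavien-Dindo score". Section 5.0 lists "complications (utilizing Clavien-Dindo classification) with an expected rate of approximately 1-2" per cent, alongside blood loss and transfusion requirements.

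On size, section 8.0 says that the power analysis "requires a total recruitment of 106 patients with 53 patients in each treatment arm", and section 4.0 allocates patients 1:1. Enrolment is set at 116 so that 106 complete.

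**The concern.** The protocol itself supplies the test, the event rate and the number of patients, and the three do not fit together. Pearson's chi-squared relies on a large-sample approximation, usually trusted when every expected cell count is at least 5. Here about one complication per arm is expected, and splitting by Clavien-Dindo grade would thin the cells further.

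Two things can follow. With no complication in either arm, the named test has no value. With a handful, the p-value depends heavily on which version of chi-squared the software applies, and the uncorrected version can fall below 0.05 where exact tests do not. Section 2.0 includes safety and a lower potential for injury among the aims, so a doubtful p-value here, in either direction, would bear on a claim that the trial wants to make.

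**Working it through.** **Inputs.** 53 completing patients per arm, 106 in total (8.0); complication rate 1% to 2% (5.0); 1:1 allocation (4.0). Assumptions: two-sided tests, and the 0.05 level of the power analysis carried over to this endpoint, since the protocol states neither for complications.

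**The plan's own figure.** The 53 per arm comes from a 10-minute difference in OR time with 80% power. No standard deviation is given, so it can only be back-solved: 10 / (1.960 + 0.842) × √(53/2) ≈ 18.4 minutes (two-sided, normal approximation). The figure can be neither confirmed nor refuted. It is taken as stated, and nothing below depends on the standard deviation.

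**Expected events.** Per arm: 53 × 0.01 = 0.53 and 53 × 0.02 = 1.06. In the whole trial: 1.06 to 2.12. With equal arms, the smallest expected cell count is half the total number of events, so reaching 5 takes at least 10 events. The probability of that is below 0.0001 at either rate.

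**No events at all.** P(no complication) = (1 − p)^106:
- 1%: 0.99^106 = 0.345
- 1.5%: 0.985^106 = 0.201
- 2%: 0.98^106 = 0.117

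The statistic is then 0/0. With all 116 enrolled patients counted, the range is 31.2% to 9.6%.

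**A split of 4 against 0, 53 per arm.** The smallest expected count is 2.0.
- Pearson, uncorrected: 106 × (4 × 53)² / (53 × 53 × 4 × 102) = 4.157, p = 0.041
- Pearson with Yates correction: 106 × (212 − 53)² / (53 × 53 × 4 × 102) = 2.338, p = 0.126
- Fisher: 2 × C(53,4) / C(106,4) = 2 × 292,825 / 4,967,690 = 0.118
- Unconditional exact tests: Barnard 0.075, Boschloo 0.063

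Only the uncorrected version is below 0.05. With 58 per arm, it gives 0.0418 against Fisher 0.1185.

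**Neighbouring splits, 53 per arm.**

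| Split | Pearson, uncorrected | Yates | Fisher |
|---|---|---|---|
| 1-0 | 0.315 | 1.000 | 1.000 |
| 2-0 | 0.153 | 0.475 | 0.495 |
| 3-0 | 0.079 | 0.241 | 0.243 |
| 5-0 | 0.022 | 0.067 | 0.057 |
| 7-1 | 0.027 | 0.066 | 0.060 |

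**False-positive rate.** Adding the binomial probabilities of all tables with p < 0.05 under equal true risk, uncorrected Pearson rejects in 0.23% of trials at a 1% rate, 0.74% at 1.5% and 1.48% at 2%. Given exactly four events, it rejects in 11.8% of trials, because only 4-0 and 0-4 reject. But four or more events occur in only 2.2% of trials at 1% and 16.3% at 2%.

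**The case against.** The case for leaving the text alone has several parts.

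- **The 0.041 depends on a choice the protocol does not make.** A reader might infer that a 4-0 split would simply be called significant. The document does not support that: it says chi-squared without naming a version, and the Yates version gives 0.126, close to Fisher. The point stands only as a conditional one, although a result that moves from 0.041 to 0.126 with a software default is itself a reason to specify.
- **Fisher is the most conservative comparator.** For 4-0 this does not matter, since Barnard and Boschloo also exceed 0.05. It does limit the other examples. A reader might infer that 5-0 and 7-1 are non-significant by any exact calculation; they are so by Fisher, but Boschloo gives 0.027 and 0.029.
- **The error rate is not inflated.** A reader might infer that it is. At the protocol's own rates, the uncorrected test rejects well under 5% of the time, and it disagrees with Fisher at 0.05 in only 0.2% to 1.4% of trials with equal risk. A 4-0 split in either direction is itself rare (0.2% to 1.2%).
- **With no events, no test says anything useful.** Fisher would merely return p = 1. This is true of the test, but a confidence interval would still give an answer.
- **The wording is not exclusive, and small-count handling often sits in an SAP.** Section 8.0 says what the analysis will include, and section 8.1 sets no hypothesis test or threshold for complications. This softens the point but does not remove it: the protocol chose a test for categorical variables and stated the rate at which that test is unsuitable.

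**Conclusion.** The point holds, as a minor one. For the complication endpoint, the test named in section 8.0 does not suit the event rate and arm size that the protocol gives. The likelier failure is a trial with no complications, where chi-squared is undefined (12% to 34% of trials). The rarer one is a sparse table such as 4-0, where the uncorrected version gives 0.041 and every exact test computed gives 0.063 or more.

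This rests on the stated 1-2% rate, 53 per arm, two-sided testing at 0.05 and, for the 0.041 only, the absence of a continuity correction. It is a fault in the p-value reported for a particular table. It does not touch the primary endpoints, laser time and OR time.

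**What to change.** In section 8.0, state that Fisher's exact test (or another exact test named in advance) will be used for complications, transfusion and any table with an expected count below 5, and that chi-squared is kept for the rest. Add that each arm's complication rate will be reported with an exact 95% confidence interval. This gives a usable answer even with no events: for 0 of 53 the upper limit is 1 − 0.025^(1/53) = 6.7%.

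The cost is a sentence or two, with no extra patients or data. The one drawback is that Fisher's test is conservative, so a borderline difference is less likely to reach significance. If that matters to the sponsor, an unconditional exact test can be named instead, provided that this is done before the data are seen.

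### The only multivariable analysis named, a Cox regression with forward selection, specifies no outcome and suits none of the stated endpoints well (minor)

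*Protocol*

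**What the plan says.** Section 8.0 of the protocol assigns "a student T-test for comparison of two continuous variables and chi-squared for categorical variables". It then adds one multivariable analysis: "If enough events occur to warrant a multivariate analysis, a Cox regression utilizing forward selection will be performed". The outcome for that model is not named.

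Section 8.1 gives the endpoints. For the primary: "The primary endpoint of interest will reduction in total laser time and total OR time". For the secondary: "Secondary endpoints will evaluate complication rates using the Clavien-Dindo score".

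Section 5.0 shows how these are measured. On laser data: "Objective data about laser settings, utilization time and total energy will be obtained at the conclusion of the case". On theatre time, "the circulating team will record the total OR time". It lists "complications (utilizing Clavien-Dindo classification) with an expected rate of approximately 1-2" per cent. It also has stone size, location and stone analysis recorded for each patient.

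The effect used for planning is expressed in minutes: "Overall OR duration may differ up to 10 min".

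**The concern.** A Cox model is built for a time to an event, usually with some patients censored, and a condition on the number of events makes sense only when events may be scarce. The stated endpoints are two durations that are complete when the case ends, and a complication rate. The preceding sentence of section 8.0 already gives each type of variable a test, so it is unclear what the Cox sentence is for.

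What is at stake is the adjusted result. On one reading the sentence does nothing. On the other it always applies and gives an answer on a scale that differs from the planned one, from a model chosen by the data. Because the text does not say which reading is meant, the choice could be made after results are seen. Meanwhile stone size and location, which are collected and plausibly related to both durations, are not put to use in an adjusted comparison in minutes.

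**Working it through.** **Matching the sentence to the endpoints**

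| Possible event | Is the condition on events informative? | Does a Cox model suit it? |
|---|---|---|
| Complication | Yes, but events are too few (below) | Poorly; section 8.1 treats complications as rates |
| End of lasering or end of the case | No; every treated patient has one | It can be fitted, but gives a hazard ratio, not minutes |

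**Expected complications**

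Inputs: 106 completers and 116 enrolled (section 8.0); a rate p of 1% to 2% (section 5.0). Expected count = N × p. P(none) = (1 − p)^N. P(5 or more) is the upper binomial tail. The protocol does not say how many events would be enough; five is used here as a lenient benchmark.

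| N | p | Expected | P(none) | P(5 or more) |
|---|---|---|---|---|
| 106 | 1% | 106 × 0.01 = 1.06 | 0.99^106 = 34% | 0.4% |
| 106 | 2% | 106 × 0.02 = 2.12 | 0.98^106 = 12% | 6.2% |
| 116 | 1% | 116 × 0.01 = 1.16 | 0.99^116 = 31% | 0.6% |
| 116 | 2% | 116 × 0.02 = 2.32 | 0.98^116 = 10% | 8.4% |

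Ten or more events in 106 patients has a probability below 0.01% at either rate.

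**The plan's own sample size**

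The 53 per arm cannot be reproduced directly, because section 8.0 states no standard deviation (SD). Solving backwards with a 10-minute difference, 80% power and two-sided alpha 0.05 (sidedness is not stated, so this is an assumption):

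- Normal approximation: SD = 10 / [√(2/53) × (1.960 + 0.842)] = 18.4 minutes.
- t distribution: SD = 18.2 minutes, used below.

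**What a linear model on the planned scale could give**

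The half-width of the 95% interval for the difference in OR time, unadjusted, is t(0.975; 104) × SD × √(2/53) = 1.983 × 18.2 × 0.194 = 7.0 minutes.

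If covariates explain a share R² of the variance, the half-width is multiplied by √(1 − R²), ignoring the few degrees of freedom spent. The protocol gives no R², so a range is assumed:

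- R² = 0.10: 7.01 × 0.949 = 6.7 minutes
- R² = 0.25: 7.01 × 0.866 = 6.1 minutes
- R² = 0.40: 7.01 × 0.775 = 5.4 minutes

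The proportional gain does not depend on the SD.

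**Forward selection**

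This part needs no arithmetic. The covariates kept are those that look predictive in the same data. The usual standard errors, p-values and intervals treat the final model as if it had been fixed in advance, so they leave out the uncertainty from choosing it.

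**The case against.** The best defence is that the sentence guards itself. It is conditional, and with one or two complications expected it will not be triggered, so nothing is lost. The unadjusted t-test in a randomised trial needs no adjusted companion. Details such as the event definition, the time origin and the candidate variables are properly left to a statistical analysis plan.

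Much of this stands. On the complications reading the sentence is close to inert. No primary conclusion depends on it. The absence of event-time details is not counted against the protocol here. But the protocol itself fixes the model and the selection method, so an analysis plan would have to follow them or depart from them. The condition gives no protection if the events are taken to be the ends of lasering or surgery.

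Three stronger readings are tempting and should be resisted.

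- *A reader might infer that a Cox model is invalid for these durations.* It is not. Uncensored times can be analysed this way. The fault is a poor match and an empty condition.
- *A reader might infer that forward selection would discard or distort the treatment effect.* The protocol does not say that treatment is a candidate for selection. If it were, failing to enter at p < 0.05 would largely restate ordinary non-significance, which the planned t-test itself has in 20% of trials at the 10-minute effect. An irrelevant covariate that enters does not in itself bias a randomised comparison.
- *A reader might infer that the condition could never be met for any event.* The calculation covers complications only. Section 5.0 also lists transfusion and stone migration without giving their rates. Neither is an endpoint in section 8.1.

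**Conclusion.** The point holds as a minor one. The Cox sentence names no outcome and suits none of the stated endpoints well. For complications it would almost never be run: 1.06 to 2.12 events are expected in 106 patients, and five or more has a probability of 0.4% to 6.2%. This rests on the protocol's own rate and on five as the benchmark. For the two durations its condition is always met, and the fit, though valid, answers in hazard ratios what section 8.0 frames in minutes. Forward selection adds a data-dependent model whose usual p-values and intervals do not reflect the selection.

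The documents do not support going further. The t-test, the chi-squared test and the sample size are untouched. The possible gain in precision for OR time rests on an SD implied by the sample size and on an assumed R².

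**What to change.** Delete the Cox and forward-selection sentence from section 8.0 and put in its place:

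> *As a supportive analysis, total laser time and total OR time will each be compared with a linear model containing treatment and the pre-specified covariates stone size and stone location, without variable selection, on a scale (minutes or log) fixed before unblinding.*

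Leave the analysis of complications in section 8.0 as it is, so that the secondary endpoint does not receive two instructions.

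The cost is one sentence. The covariates are already collected under section 5.0, and neither the primary t-test nor the sample size changes. The downside is that the form of the covariates and the scale must be settled in advance, and a log scale would give a ratio of times, not a difference in minutes. If the sponsor wants no adjusted analysis, deleting the sentence alone removes the mismatch but gives up the possible gain in precision.

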8.1 Endpoint Considerations

The primary endpoint of interest will reduction in total laser time and total OR time. Secondary endpoints will evaluate complication rates using the Clavien-Dindo score.

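### Two outcomes are primary in Section 8.1, but the single alpha, power and sample size in Section 8.0 mention a difference for OR time only

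*Protocol*

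**What the plan says.** Section 8.1 defines the primary endpoint in one sentence: "The primary endpoint of interest will reduction in total laser time and total OR time". The next sentence places only complications below it: "Secondary endpoints will evaluate complication rates using the Clavien-Dindo score". Nothing ranks the two times or says whether one or both must show a reduction.

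The two times are not parts of a single score. Section 5.0 takes laser data at the end of the case ("Objective data about laser settings, utilization time and total energy will be obtained at the conclusion of the case") and has OR time come from a different source ("the circulating team will record the total OR time").

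Section 8.0 opens its sample-size paragraph with OR time: "Overall OR duration may differ up to 10 min with an average OR time for URS estimated at approximately 1 hour". It continues: "A power analysis with 80% power and an alpha of 0.05 requires a total recruitment of 106 patients", which is 53 per arm. For the analysis it states: "Statistical analysis of the obtained data will include a student T-test for comparison of two continuous variables". It gives no difference, mean or SD for laser time, and does not say which outcome entered the power analysis.

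**The concern.** The endpoint section and the sample-size section should describe the same objective. Here one has two parts, and the other has one power figure and one anticipated difference. A single 80% and a single 5% have a clear meaning for one outcome tested once. For two outcomes their meaning depends on the success rule, and Section 8.1 gives none.

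The practical risk is a split result. Laser time is only part of OR time, so a clear reduction in laser time without a significant reduction in OR time is quite possible. The protocol would not then say whether the trial met its primary objective. If that is settled after the data are seen, the choice itself costs error control.

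**Working it through.** **Inputs from the protocol.** Alpha 0.05, power 80%, 53 per arm, OR-time difference up to 10 minutes, Student t-test (Section 8.0); two primary outcomes (Section 8.1). **Assumed, because not given:** two-sided testing, laser-time power, and the correlation between the two test statistics (shown over 0 to 0.9).

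**1. The plan's own figure.** No SD is stated, so 53 per arm can only be back-solved. SD = 10 × √(53/2) / (1.960 + 0.842) = 51.48 / 2.802 ≈ 18.4 minutes (18.2 with the t distribution). The figure is thus compatible with an OR-time calculation, but this does not prove that it was one.

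**2. Either outcome suffices, each tested two-sided at 0.05.** Family-wise error = 1 − P(|Z1| < 1.96 and |Z2| < 1.96), bivariate normal. At correlation 0 this is 1 − 0.95² = 0.0975.

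| Correlation | 0 | 0.5 | 0.7 | 0.9 |
|---|---|---|---|---|
| Family-wise error | 9.75% | 9.1% | 8.3% | 7.0% |

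**3. Both outcomes required, each tested at 0.05.** The probability of a false claim stays at or below 5%. Joint power = P(Z1 < z(0.80) and Z2 < z(laser-time power)), bivariate normal. It cannot exceed the smaller single power, so 80% is the ceiling if the stated 80% belongs to either outcome. At correlation 0 with 80% for each it is 0.80 × 0.80 = 0.64.

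| Assumed laser-time power | Corr. 0 | 0.5 | 0.7 | 0.9 |
|---|---|---|---|---|
| 80% | 64.0% | 68.7% | 71.3% | 75.0% |
| 90% | 72.0% | 75.2% | 76.9% | 79.1% |
| 95% | 76.0% | 77.9% | 78.9% | 79.9% |
| 99% | 79.2% | 79.7% | 79.9% | 80.0% |

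The correlation-0 column is an edge case, since laser time is contained in OR time. For given single-outcome powers, the table does not depend on the SDs, and it is symmetric if the 80% belongs to laser time instead.

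**4. A favourable structural case (assumption).** Suppose the whole OR-time difference is saved laser time and the rest of the case varies independently. Let k be the laser-time SD divided by the OR-time SD. The correlation is then k, and the standardised laser-time effect is 1/k times that for OR time. Laser-time power is Φ(2.802/k − 1.960). At k = 0.5 it exceeds 99.9% and joint power is 80.0%; at k = 0.8 it is 93.8% and joint power 79.2%; at k = 0.95 it is 83.9% and joint power 78.3%. Under this model almost nothing is lost.

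**5. Fixed order.** If OR time is tested first at 0.05, and laser time at 0.05 only after success, family-wise error is at most 5% at any correlation. Power for OR time is the power of a single test at 0.05.

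**The case against.** The strongest reply is that Section 8.1 is one ungrammatical sentence listing two times of interest, and that Section 8.0 shows what was meant: OR time was powered and laser time is reported beside it. On that reading no power is lost. A testing order or success rule may also stand in a statistical analysis plan that is not shown, and its absence from the protocol alone would be no finding. Both points limit the consequence. They do not remove the mismatch: the protocol itself calls both outcomes primary and makes only complications secondary, while its sample-size section mentions a difference for one of them.

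A reader might infer more than this, and the documents do not support it:

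- **That the joining word in Section 8.1 is a both-must-succeed rule.** The sentence names outcomes; it does not state a decision rule.
- **That the trial runs at nearly 10% error.** That needs either outcome to suffice, unadjusted two-sided tests and no correlation. The protocol does not say that either suffices, and an analysis plan may rule it out.
- **That power is really 64%, a loss of 16 points.** That needs zero correlation and an assumed laser-time power of only 80%. The protocol's rationale, that faster fragmentation shortens laser time and thereby the case, points the other way, as step 4 shows. If laser time explains only part of the OR-time difference and varies widely, the loss could be larger than in step 4.
- **That laser time must be almost certain to reach significance.** At correlation 0.9, laser-time power of about 86% already keeps joint power at 78%.

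**Conclusion.** The concern stands as a mismatch between two sections. Two outcomes are primary, without order or success rule, and the 5%, 80% and 53 per arm are single figures set beside a difference for OR time only. Those figures therefore do not describe the primary objective as written.

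The consequence depends on the rule. If either outcome suffices without adjustment, error exceeds 5%. If both are required, error is held, but power is at most 80% and falls short of it by anything from almost nothing to about 11 points at correlation 0.5 (80% − 68.7%), or up to about 5 points at 0.9 (80% − 75.0%). These ranges rest on assumed laser-time power and correlation. Without laser-time inputs the actual loss cannot be determined, and it may be negligible. Confidence is high in the mismatch and low in any single figure for its effect. It should be fixed, because the correction is nearly free and has to be made before the data are seen.

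**What to change.** Set a fixed testing order in Section 8.1 before any data are seen. The choice that matches Section 8.0 is total OR time as the single primary endpoint and total laser time as the first secondary, tested at 0.05 only if OR time is significant. Section 8.0 should confirm that OR time was the outcome in the power analysis, which is the natural reading. If so, alpha stays at 5%, the stated 80% stands, and no patients are added. The cost is one or two sentences. The downside is that laser time has no confirmatory claim if OR time fails.

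Equally acceptable, if the sponsor wants laser time first or both required: state that rule in Section 8.1, give the laser-time difference and SD in Section 8.0, and restate the power that 53 per arm delivers for that objective. With laser time first, OR time has no confirmatory claim if laser time fails. With both required, neither has one unless both succeed, and holding 80% joint power may need more patients. As an illustration, with effect sizes back-solved from 53 per arm and laser-time power of 80%, 90% or 95% at that size, the need is 66, 59 or 56 per arm at correlation 0.5, and 60, 55 or 54 at 0.9. That is 1 to 13 more per arm.
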